***Hypothesis 1:** Two weeks of at-home practice will result in better performance of respiratory control (maintenance of frequency and volume over time) in those who practice more, however, accurate performance of yogic breathing will be lesser in those with high thoracic injuries (T3-T6).*

***Objective 2:** To assess the respiratory and hemodynamic changes that accompany slow yogic breathing in spinal cord injury patients.*

***Hypothesis 2:** Respiratory rate will decrease, blood pressure will decrease, tidal volume will increase, and minute ventilation will remain unchanged during yogic slow breathing compared to spontaneous breathing.*

***Objective 3:** To discern the changes in the relationship between respiration, heart rate and blood pressure variabilities with yogic breathing.*

***Hypothesis 3:** Slow yogic breathing will shift the relationship between heart rate and blood pressure variabilities toward more synchronized heart rate and systemic blood pressure fluctuations.*

3. General Description of Study Design

This study will be a small (N= 20) prospective cohort study with a one-time unblinded intervention of 4 differing breathing techniques compared to paced breathing. Participants will receive a log for at-home practice and instruction lasting 45 minutes around D1 and D7 with the option to have on coaching session via MGB's Zoom application. On D14 the participant will be asked to sequentially execute the randomized breathing techniques. The lab visit will last approximately 1.5 hours, during which beat-by-beat

cardiovascular variables and breath-by-breath respiratory variables will be recorded while slow breathing. The total in-person time commitment is about 4 hours (**Figure 2**).

[figure not shown]

Figure 2: Study schema with a timeline of participant contact hours and days. There will be two moments of coached practice during a period of two weeks with at-home practice encouraged throughout the period. At the conclusion of the two weeks the breathing practices will be repeated in the laboratory while obtaining respiratory and cardiovascular measurements. *It is possible for the participants to schedule the second visit via MGB's Zoom application.

4. Subject Selection

a) Inclusion/Exclusion Criteria

We will complete studies on 20 individuals — men and women aged 18 to 60 years — with a spinal cord injury. A detailed medical history will be taken, and subjects will be selected based on the following:

Inclusion criteria:

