- 1) History of Spinal Cord Injury
- 2) Age: 18-60 years old
- 3) Wheelchair user
- 4) Medically stable & able to follow directions
- 5) Body mass index (18.5 - 35 kg/m²)

Exclusion criteria:

- 1) BP >140/90 mmHg
- 2) Current use of tobacco or cardioactive medications (except medication to support blood pressure)
- 3) Significant arrhythmia
- 4) Coronary artery disease
- 5) Diabetes
- 6) Renal Disease
- 7) Cancer
- 8) Epilepsy or other neurological diseases
- 9) Non-English Speakers

Source of subjects and recruitment methods

All volunteers will be considered regardless of race, ethnicity, or national origin. We plan to study both men and women. We will recruit individuals with a spinal cord injury from the Exercise for Persons with Disabilities (ExPD) program at Spaulding Hospital Cambridge.

Research Assistants will identify eligible individuals during scheduled ExPD workout sessions and from population of past ExPD participants. Where possible eligible individuals will be given a flyer. If the ExPD population is exhausted before reaching our desired number of participants, recruitment can be extended to the general SCI population of Boston via the use of flyers. If eligible and interested participants will be asked to complete a pre-screening phone survey.

5. Subject Enrollment

The principal or co-investigators will obtain volunteer consent in accordance with guidelines established by the Institutional Review Board during the first study visit to the Cardiovascular Laboratory. Participants are encouraged to ask questions and are reminded that participation is strictly voluntary and will not affect their current or future care at Spaulding Rehabilitation Hospital or any of its affiliates. Each subject will be told that he/she will be free to discontinue participation in the experiment at any time and that the investigators reserve the right to discontinue the research protocol at any time. A copy of the signed informed consent form will be given to the subject. All study subjects will participate in the same study protocol, differing only by the randomization of the order of the yogic breathing techniques.

6. Study Procedures

a) Study Components

YOGIC BREATHING INTERVENTION

The subject will receive one-on-one coaching on breathing techniques with the co-investigator two times. The subject may opt to complete the second coaching session via MGB's Zoom application.

The breathing techniques will be varied in:

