Two weeks after inclusion, the subjects will return to the cardiovascular laboratory for assessments. All subjects will be instructed to abstain from vigorous exercise for 1 day prior to each study to avoid autonomic and neuroendocrine effects of exercise. In addition, subjects will refrain from caffeine and alcohol for the previous 24 hours and be studied at least 2 hours after a meal. All breathing patterns and techniques will be practiced with the participant before the day of measurement and the participant will also be coached by a pre-recorded audio track during measurement.

Measurements

1) Pulmonary function test

All subjects will perform standard spirometry for spinal cord injury, as describe in (44). The same technician will test all subjects. Subjects will be seated with belts or pant waists loosened and with a nose clip. The maneuver will be demonstrated, and instructions will be given to inhale completely and "blast" the air out. The subject will be encouraged to exhale maximally and sustain the effort at least 6 sec or longer, if possible, depending on the ability and willingness of the subject to continue. The volume-time curve will be recorded on a kymograph, and the flow-volume loop will be electronically displayed for review. An acceptable effort will be a minimum exhalation time of 6 sec with a rapid start and a well-defined early peak in flow that is smooth and continuous. Three acceptable efforts will be obtained.

2) CV Lab Measurement

Throughout the protocol, subjects will lie 30° supine and will be instrumented with a 5-lead EKG, pulse oximeter, finapress with sphygmomanometer, doppler, chest and abdominal belts, a microphone and a face mask with a two-way respiratory valve; for measurements of QRS-complex, SpO₂,

beat-by-beat arterial pressure, brachial blood flow, respiratory excursions, ujjayi sound mixed expired CO₂, ventilation and end-tidal CO₂.

After instrumentation and calibration, the subject will undergo a period acclimation with a resting breathing pattern for ~7 minutes. We will then record the breathing techniques for ~7 minutes each. Other than the acclimation period with resting breathing frequency the order of the other 5 breathing patterns will be randomized. Upon completion subjects will be asked to turn-in their two-week breathing logs. Participants will proceed to perform an exit-PFT and will then be finished with their contribution to the study.

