Data analysis will begin with summary of important variables. Continuous data will be summarized using means and standard deviations, and categorical data will be summarized using frequencies and proportions. Spectral analysis will be used when appropriate. Mean values for these variables will be compared within subjects using t-tests or Wilcoxon Rank Sum tests. Effects of the important covariates including age, BMI, time since injury, and level of injury will be adjusted for via regression analysis. Co-variables will be compared using a t-test or Wilcoxon Rank Sum test in case of continuous variables and they will be compared using chi-squared test and Fisher's Exact test. Significant co-variables will be used in the above regression analysis.

10. Monitoring and Quality Assurance

As these studies represent physiologic investigation and not clinical trials, no formal quality assurance programs will be implemented but will be overseen by the principal and co-investigators.

Safety

All volunteers will be thoroughly screened prior to study. Studies are conducted in a well-supervised hospital facility and subjects are under constant observation by skilled professionals. Appropriately trained laboratory personnel are present during the procedures and continuous cardiovascular monitoring is performed. Procedures are stopped if the volunteer exhibits potentially serious side effects. In the event of adverse reactions or emergency, resuscitation equipment and medical care are immediately available at Spaulding Rehabilitation Hospital. All volunteers are provided a contact number should there be any complications following study.

Adverse Events

Any adverse events will be promptly reported to the Human Research Committee for review according to HRC guidelines. Serious adverse events either expected or unexpected will be reported immediately (within 24 hours of event) by telephone, fax or email followed by a full written report using the PHRC Adverse Event Form within 10 working days/14 calendar days. Mild to moderate unexpected or expected adverse events will be reported in writing using the PHRC Adverse Event Form within 20 working days/30 calendar days.

Confidentiality

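### Section 9 names the Wilcoxon rank-sum test, which assumes independent samples, for comparisons made within the same 20 participants; used as written, it discards the pairing

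*Combined protocol and SAP*

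**What the plan says.** Section 9, Data analysis, gives one rule for comparing conditions: "Mean values for these variables will be compared within subjects using t-tests or Wilcoxon Rank Sum tests". Shortly afterwards it names the same pair of tests for a different purpose: "Co-variables will be compared using a t-test or Wilcoxon Rank Sum test in case of continuous variables". It does not say which groups that second comparison involves.

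The design is set out elsewhere in the same document:

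- Section 4 gives a single group: "We will complete studies on 20 individuals".
- Section 5 has no parallel arm: "All study subjects will participate in the same study protocol, differing only by the randomization of the order of the yogic breathing techniques".
- Section 6 (CV Lab Measurement) has each person record resting breathing and then the other patterns in one session: "Other than the acclimation period with resting breathing frequency the order of the other 5 breathing patterns will be randomized".
- Section 2, Hypothesis 2, contrasts yogic slow breathing with spontaneous breathing for respiratory rate, blood pressure, tidal volume and minute ventilation.

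The document states no alpha, power, effect size, standard deviation or within-person correlation.

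**The concern.** The rule contradicts itself. It asks for a within-subject comparison and then offers a test for two unrelated samples. The rank-sum (Mann-Whitney) test pools all 40 values of a two-condition contrast, ranks them without regard to who produced them, and judges the shift against a null distribution that is valid only if the two sets of 20 are independent.

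Here they come from the same people. Differences between people that persist across conditions are removed when each person serves as their own control, but the rank-sum test keeps them as noise. The document itself lists age, BMI, time since injury and injury level as important covariates. All are fixed within a person during the session. As far as they affect the outcomes, they make within-person correlation positive.

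The risk is that real changes in blood pressure or ventilation are reported as non-significant in a study of 20 people with no power calculation to show how much loss it could absorb.

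**Working it through.** **No stated figure to reproduce.** The plan gives N = 20 without a power calculation, so the check shows what the named test does to paired data of this size.

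**Inputs**

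- From the documents: 20 participants, each measured under both conditions of any contrast.
- Assumed: two-sided alpha 0.05, bivariate normal outcomes, equal standard deviations (set to 1), and within-person correlation ρ from 0 to 0.8.

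**Direction of the error.** For a difference between two condition means, the true variance is 2σ²(1 − ρ)/n. An independent-samples test takes it to be 2σ²/n. Under the null, the test statistic therefore has a standard deviation of about √(1 − ρ) rather than 1, and the actual two-sided error rate is roughly 2 × [1 − Φ(1.96/√(1 − ρ))].

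- ρ = 0.3: 1.96/√0.7 = 2.34, giving about 1.9%.
- ρ = 0.5: 1.96/√0.5 = 2.77, giving about 0.6%.
- ρ = 0.7: 1.96/√0.3 = 3.58, giving about 0.03%.

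This is a large-sample approximation for means. The rank-sum test follows the same pattern, and the simulation gives its values directly.

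**Effect used for power.** With n = 20, the paired t-test has 80% power at a standardised paired difference of 0.66 (noncentral t, 19 degrees of freedom). In units of the outcome's standard deviation, the shift is d = 0.66 × √(2(1 − ρ)). At ρ = 0.5, d = 0.66 × 1 = 0.66. At ρ = 0.8, d = 0.66 × √0.4 = 0.42.

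**Results.** Ranges show the spread between separate simulation runs.

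| ρ | Shift d (SD) | Rank-sum power | Rank-sum type I error at nominal 5% |
|---|---|---|---|
| 0 | 0.93 | 80% | about 5% |
| 0.3 | 0.78 | 67% | about 2% |
| 0.5 | 0.66 | 51–52% | 0.8–1.0% |
| 0.6 | 0.59 | 40% | 0.4–0.5% |
| 0.7 | 0.51 | 25–27% | about 0.2% |
| 0.8 | 0.42 | 10–11% | about 0% |

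On the same footing, signed-rank power is about 77–79% at every ρ, and its error rate stays close to 5%.

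**Reading the table.** Half of the signed-rank power is about 78/2 = 39%, so rank-sum loses more than half only above a correlation of roughly 0.6. At 0.5 it loses about a third: (78 − 51)/78 = 35%. At 0 it loses nothing.

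**Larger effects.** The table fixes the effect at 80% paired power. With ρ = 0.7 and a shift of 0.8 SD instead of 0.51, rank-sum has about 77% power and signed-rank about 99%. The gap narrows from about 52 points to about 22.

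**The case against.** The strongest reply is that this is a slip in a name. The sentence says the comparison is within subjects, so signed-rank was probably meant, and a competent analyst would run it. The harm also needs two steps: choosing the non-parametric option, and running it literally. That is fair as to likelihood. It does not remove the error, because the only non-parametric test the plan names for these contrasts is the wrong one and nothing else in the document corrects it.

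Four stronger readings are tempting, and the documents do not support them:

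- **That most of the power is lost.** This holds only at higher correlations, which the documents do not give, and the loss shrinks for large effects. It will also differ by outcome. Section 6 makes breath frequency one of the features that the techniques vary, so respiratory rate is largely imposed and may show a large shift.
- **That the t-test is wrong too.** The sentence already describes the t-test as within subjects, which reads as a paired test. The word is missing, but the instruction is there.
- **That the slip wrongly confirms Hypothesis 2 on minute ventilation.** That hypothesis says "minute ventilation will remain unchanged during yogic slow breathing compared to spontaneous breathing", and p-values that are too large do lean that way. But reading non-significance as no change is unsound with the signed-rank test as well. It is a separate problem, and correcting the test name does not cure it.
- **That a baseline-versus-exit lung function comparison is affected.** Section 9 states no such comparison.

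Nor is every mention of the rank-sum test a fault. For co-variables compared between independent groups it could be the right test.

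**Conclusion.** Wrong as written. The rank-sum test is not valid for comparing conditions within the same 20 people. With positive within-person correlation, its p-values are too large and it can lose a substantial share of the power. The error is conservative in that case, so it hides real differences and does not create false ones.

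The existence of the fault follows from the text alone. Its size does not. It rests on the assumed correlation, on normal data with equal spread, and on an effect set at 80% paired power. Under those assumptions the cost runs from nothing at correlation 0 to almost 70 points of power at 0.8. High correlation is plausible for recordings made in one session, but that remains an assumption. The finding is confined to the non-parametric option.

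**What to change.** In the Section 9 sentence on within-subject comparisons, replace the two test names with *paired t-tests or Wilcoxon signed-rank tests*. Adding *paired* only clarifies what the sentence already implies; *signed-rank* is the correction. Keep the rank-sum test only for comparisons between independent groups, and say so where the co-variable comparison is described.

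The cost is one phrase, with no new data and no change to study procedures.

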Note: Subjects that completed Lab Visit 3 before 5/19/23 will be invited back to repeat Lab Visit 3 with the addition of dead space ventilation measurements that has been added to this protocol.

7. Risks and Discomforts

The proposed study will utilize non-invasive cardiovascular and respiratory monitoring techniques with minimal risks. The attachment and removal of ECG electrodes and inflation of the blood pressure cuff may cause mild discomfort. Slow breathing may cause hypercapnia and lightheadedness, which quickly resolves when normal breathing resumes.

8. Benefits

a. Benefits to Participating Individuals

There are no direct benefits other than increased knowledge of different traditional breathing practices and their mental and physical effects.

Financial Compensation

Participants in this study will be compensated financially up to \$100USD relative to their time. As completion of all study visits is necessary for analysis participants will be paid \$20 for each study visit they complete. Payments will be made via check and participants SSN will be collected.

Note: Subjects that have already completed the protocol and repeat the LabVisit 3 protocol will be paid \$20 for this additional visit.

b. Benefits to Society

This research may help physicians and scientists to better understand how slow breathing patterns influence the cardiovascular system in persons with SCI, potentially informing future interventional studies in this population.

9. Statistical Analysis

Specific data variables being collected: We will collect data on RR interval, heart rate, blood oxygenation, beat-to-beat blood pressure, brachial blood flow, breathing frequency/depth, ventilation volumes and end-tidal carbon dioxide levels.

b) Data analysis

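### Five breathing patterns are run in randomised order, but Section 9 plans separate two-condition tests with no period term, principal outcome or multiplicity control, and names an independent-samples rank test for paired data

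*Combined protocol and SAP*

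**What the plan says.** The design (Section 3) is a "one-time unblinded intervention of 4 differing breathing techniques compared to paced breathing", with 20 participants. Under Visit 3 in Section 6, a resting acclimation block of about 7 minutes is followed by blocks of about 7 minutes each: "Other than the acclimation period with resting breathing frequency the order of the other 5 breathing patterns will be randomized". Section 5 says that participants follow one protocol, "differing only by the randomization of the order of the yogic breathing techniques".

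Section 9 opens its list of variables with "We will collect data on RR interval, heart rate, blood oxygenation, beat-to-beat blood pressure, brachial blood flow" and goes on to breathing frequency and depth, ventilation volumes and end-tidal carbon dioxide. The comparison of conditions rests on one sentence: "Mean values for these variables will be compared within subjects using t-tests", with the Wilcoxon Rank Sum test as the alternative. A regression on age, BMI, time since injury and level of injury follows.

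Section 9 does not state a period or sequence term, a model for the repeated measurements, a principal outcome, the pairs of conditions to be tested, a significance level or a rule for multiple testing. The comparator also differs between sections. Section 3 uses paced breathing, whereas Hypothesis 2 in Section 2 is framed against rest, for example "minute ventilation will remain unchanged during yogic slow breathing compared to spontaneous breathing".

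**The concern.** A session with five randomised periods is a crossover, and the planned analysis does not use that structure. Four consequences follow.

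- **Precision.** If heart rate, pressure or CO2 drifts over the session, a paired difference between two patterns also carries the difference in their positions. A period term removes that part; a plain paired test leaves it in the error.
- **Selection.** With several contrasts, eight or nine variables and no named principal result, a reader cannot tell a planned finding from the best of many.
- **Wrong test.** Rank sum ignores the pairing that makes a 20-person within-subject study workable.
- **Rest as comparator.** Rest is always first, so any difference from rest mixes the effect of breathing with the effect of time.

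The planned regression fills none of these gaps. Its covariates are constant within a participant, so their main effects cancel in a within-subject difference, and none of them is period.

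**Working it through.** The documents give no alpha, power, SD or sample-size calculation, so there is no figure of theirs to reproduce.

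**Inputs from the documents.** N = 20 (Section 3). Six conditions, of which five are randomised (Section 6); I read these as the four techniques plus paced breathing of Section 3. Variables: 8 listed items, or 9 if breathing frequency and depth are counted separately (Section 9). Contrasts under Section 3: four techniques against paced breathing.

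**Assumptions.** Two-sided alpha 0.05. Linear drift *d* per block, in units of the within-person SD. Correlation between variables from 0 to 0.7.

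**1. False positives, one outcome.** If four tests were independent: 1 − 0.95^4 = 18.5%. The four share the paced comparator, and simulation of paired t-tests at N = 20 gives about 16%. For all 15 pairs of six conditions, simulation gives about 38%.

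**2. False positives, nine variables.** 9 × 4 = 36 tests. Expected false positives if nothing differs: 36 × 0.05 = 1.8. Upper figure under independence: 1 − 0.95^36 = 84%. Simulation with the shared comparator gives about 79% with uncorrelated variables, falling to about 74%, 66% and 54-55% at correlations of 0.3, 0.5 and 0.7. The range is therefore roughly 55-84%.

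**3. Precision lost by omitting period.** In a random order of five slots, each position has variance (25 − 1)/12 = 2 and two positions have covariance −2/4 = −0.5. The difference in position then has variance 2 + 2 + 2 × 0.5 = 5. Without drift a paired difference has variance 2 SD², so the inflation is 1 + 5*d*²/2.

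| Drift per block (SD) | Variance inflation | Square root | Simulated CI width, paired t ÷ period-adjusted |
|---|---|---|---|
| 0 | 1.00 | 1.00 | about 1.01 |
| 0.2 | 1.10 | 1.05 | about 1.06 |
| 0.4 | 1.40 | 1.18 | about 1.20 |

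The simulated ratios also reflect the different error degrees of freedom (19 for the paired test, 72 for the model). Type I error of the paired t-test stayed near 5% at every drift.

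**4. Contrasts with rest.** Put rest in slot 0. A randomised pattern has mean slot (1+2+3+4+5)/5 = 3, so linear drift shifts every contrast with rest by 3*d* on average: 0.6 SD at *d* = 0.2 and 1.2 SD at *d* = 0.4. This is bias, not noise. Rest never occupies another slot, so a period term cannot separate the two effects.

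**5. Rank sum on paired data.** Take a standardised paired difference of 0.66, for which the paired t-test has 80% power at N = 20. Rank sum has about 66%, 52%, 25% and 1% power at within-subject correlations of 0.3, 0.5, 0.7 and 0.9. Signed-rank keeps 77-81%.

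**6. Price of error control.** With one principal outcome and four contrasts, the Bonferroni level is 0.05/4 = 0.0125. The difference detectable with 80% power rises from 0.66 to 0.82 SD of the paired difference. Correcting all 36 tests (0.05/36 = 0.0014) would raise it to about 1.05, which is why naming a few contrasts is preferable to correcting everything.

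**The case against.** Section 10 calls the work physiologic investigation, and Section 8 presents it as informing later interventional studies. On that view formal error control is out of place, and calling the analyses exploratory would be enough. Much of this stands for the secondary variables. It does not cover the three stated hypotheses, which are directional and will be read as tested.

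Several stronger readings are tempting, and the documents do not support them.

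- **Chance findings are near certain.** That needs something close to all 15 pairs on weakly correlated variables, and no section plans this. RR interval and heart rate are nearly the same measurement, and the technique sets the breathing frequency, so nine variables are not nine separate null tests.
- **The tests are invalid because order is ignored.** Randomisation protects contrasts among the five patterns. The cost is precision, and it is modest unless drift is large.
- **The slots will be badly unbalanced.** Section 6 says only that order is randomised. A restricted or balanced scheme is not excluded.
- **Blocks run back to back, so carry-over is built in.** No gap is stated, but six blocks of about 7 minutes fill 42 of roughly 90 minutes. Carry-over is possible but not established.

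A fair technical objection is that a model with one residual variance can itself mislead. As an illustration with assumed SDs, if one technique has twice the residual SD of the others, its nominal 5% contrast rejects about 12% of the time, while the paired t-test stays at 5%. The fix allows for this.

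**Conclusion.** The point holds as a should-change item. Section 9 leaves the randomised order out of the analysis, names no principal outcome or contrast, controls no error rate, and offers an independent-samples test for paired data.

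The chance of a false positive is about 16% for the four paced contrasts on one outcome and roughly 55-84% over nine variables. Both rest on an assumed alpha of 0.05, and the second also on the correlation between variables. The 1-20% loss in interval width rests on an assumed linear drift of up to 0.4 SD per block. Two parts need no assumed figure: rank sum does not suit within-subject data, and contrasts with rest are confounded with time. The second matters most for Hypothesis 2, whose wording makes rest the comparator.

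**What to change.** Rewrite the data-analysis part of Section 9 as follows.

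1. For each outcome, analyse the five randomised patterns with a within-participant model containing pattern and period (1-5). Either allow the residual variance to differ by pattern, or report paired contrasts as a sensitivity check.
2. Name one principal outcome per hypothesis and state alpha. Apply Holm or Dunnett to the four yogic-versus-paced contrasts, and label everything else exploratory.
3. Reconcile the comparator between Section 3 (paced) and Hypothesis 2 (spontaneous). The model in item 1 does not include rest, so it cannot test Hypothesis 2 as worded. Report any contrast with rest as open to confounding with time.
4. Replace rank sum with the Wilcoxon signed-rank test for within-subject comparisons.

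Optionally, use a balanced list of orders for participants not yet measured. Exact balance should not be claimed: Section 6 provides for participants who completed Visit 3 before the date of this version, and their orders are already fixed.

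The cost is a change of wording, plus an order list if the option is taken. No visits or participants are added, and the model also works with orders already used. The downside is that some secondary p-values become less favourable, and the principal contrasts face a stricter threshold (detectable difference about 0.82 rather than 0.66 SD under Bonferroni).

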1. breath frequency (between 0.25 and 0.08 Hz)
2. Inspiratory – Expiratory ratio (I:E) or 'Duty Cycle'
3. with and without ujjayi (yogic throat constriction)
4. with and without inspiratory/expiratory breath holding

AT-HOME PRACTICE

At the end of the first visit the subject will be given a log to record their at-home practice of the breathing techniques they were coached on. Participants will also receive an information pamphlet and audio track with information about the exercises covered during the first coaching session.

b) Study Visits

Pre-Screening

All study subjects from the ExPD program at Spaulding Hospital will be preliminarily screened over the telephone to ensure that they meet preliminary eligibility requirements. Eligible members will be approached after their workouts by the co-investigator to ask permission to call for screening.

Screening

Subjects who meet preliminary eligibility criteria and are interested in participating will be called by the co-investigator to screen inclusion and exclusion criteria and to discuss additional information about the study. Participants will be sent the informed consent letter at least one week before the first visit. Informed consent will be obtained at Spaulding Rehabilitation Hospital, Cambridge.

Visit 1 — History, Baseline, 1st Coaching

During participants first visit the study procedures will be reviewed in detail with study staff, the subject will give a detailed health history and their written informed consent to the principal or co-investigator. The participant will then proceed to complete a baseline pulmonary function test (PFT) lasting about 30 minutes. Leaving about 45 minutes to cover relevant breathing techniques and exercises.

Visit 2 — 2nd Coaching

The second coaching visit can optionally be completed via MGB's Zoom application and will be shorter and more focused on questions, concerns, or struggles of the participant.

Visit 3 — Breathing & Measurement

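### Section 9 compares mean values within subjects, so it does not test Hypothesis 1, which concerns holding the breathing pattern over time in people who practise more

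*Combined protocol and SAP*

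**What the plan says.** Section 2, Hypothesis 1, defines performance in its own words. After two weeks at home there will be "better performance of respiratory control (maintenance of frequency and volume over time) in those who practice more", with less accurate performance expected in high thoracic injuries.

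The data can show this. Section 3 says that "cardiovascular variables and breath-by-breath respiratory variables will be recorded while slow breathing", and the CV Lab Measurement text in Section 6 adds "We will then record the breathing techniques for ~7 minutes each". Section 6 also has participants keep a log of home practice and follow a pre-recorded audio track during measurement.

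Section 9 lists the variables, among them "breathing frequency/depth, ventilation volumes and end-tidal carbon dioxide levels". Under Data analysis it says "Continuous data will be summarized using means and standard deviations", then "Spectral analysis will be used when appropriate", then gives the one stated comparison: "Mean values for these variables will be compared within subjects using t-tests or Wilcoxon Rank Sum tests". Regression adjusts for covariates, of which age, BMI, time since injury and level of injury are named. Home practice is not named. No section defines a measure of maintenance or accuracy.

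**The concern.** There are two mismatches between Hypothesis 1 and the stated analysis.

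- **Outcome.** The hypothesis is about keeping frequency and volume steady through a recording. The quantity tested is a mean, which is the same whatever order the breaths come in.
- **Contrast.** The hypothesis compares people by how much they practised. The cued patterns are recorded only at Visit 3, so this is a between-person comparison. A within-subject test compares one pattern with another in the same person and does not involve practice.

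Without a stated measure, the study must either report something that does not answer Hypothesis 1 or choose a maintenance measure after seeing the data of 20 participants. The second course would make the result post hoc.

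**Working it through.** The documents give no effect size, SD or power for Hypothesis 1, so there is no stated figure to reproduce. The drift patterns and SDs below are assumptions.

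**Inputs from the documents.** N = 20 (Section 3). Recordings last about 7 min = 420 s, and frequencies run from 0.25 to 0.08 Hz (Section 6). Breaths per recording = frequency × 420: 0.25 × 420 = 105, 0.10 × 420 = 42, 0.08 × 420 = 33.6.

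**Step 1: same mean, different maintenance.** Suppose the cue is 0.08 Hz. One person holds it. Another drifts linearly from 0.06 to 0.10 Hz (assumed, ±25%).

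- Average frequency of the drifter: (0.06 + 0.10)/2 = 0.08 Hz, equal to the cue.
- Counting whole breaths, both complete 33 in 7 min. Breaths divided by elapsed time are 0.0800 and 0.0792 Hz, 1% apart.
- RMS deviation from the cue is 0 for the first. For the second it is approximately range/√12 = 0.04/3.464 = 0.0115 Hz, or 0.0115/0.08 = 14% of the cue.

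**Step 2: what the SD adds.** For the drifter, the per-breath mean is 0.0809 Hz and the SD 0.0116 Hz. Shuffling the breaths changes neither, yet frequency from the first to the last third is 0.067 to 0.094 Hz in the true order and 0.081 to 0.075 Hz when shuffled. A within-recording SD shows that frequency was not constant, but not that it drifted.

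**Step 3: why RMS deviation is more robust.** With the SD taken over the breaths of one recording (divisor = number of breaths),

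RMS² = (mean − cue)² + SD².

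The mean carries only the first part and the SD only the second. RMS deviation carries both.

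**Step 4: illustration of power.** Assume 20 participants, 42 breaths at a cue of 0.10 Hz, total drift averaging 0.02 Hz and falling 0.01 Hz per SD of practice, residual SD 0.01 Hz, and breath noise SD 0.005 Hz. Each measure is related to practice at two-sided 5%, without injury level in the model.

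| Assumed drift | Mean frequency | Signed slope | RMS deviation |
|---|---|---|---|
| Symmetric about the cue | 4-5% | 95% | 91-93% |
| All one way, starting at the cue | 95-96% | 92-96% | 91-93% |
| Starting at the cue, direction varies by person | 8-9% | 8-9% | 91-93% |

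The small ranges come from repeated runs and, for the signed slope in the second row, from breath noise of 0.003-0.01 Hz. Under symmetric drift and that same range of noise, the within-recording SD has 78-93% power, and RMS deviation is about the same.

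**The case against.** **Section 9 offers more than a mean.** This is correct. It also names SDs and spectral analysis, so a reader who infers that every recording is reduced to a mean goes too far. But the level of the SD (within a recording or across people) is not stated, the spectral analysis has no variable or index attached, and neither is linked to Hypothesis 1.

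**The covariate list is open-ended, so practice could be added.** It could. The plan does not say so, and the regression is described as adjustment of the mean comparisons, so the outcome would still be a mean.

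**The pulmonary function tests at Visits 1 and 3 cover Objective 1.** They may bear on respiratory fitness. They do not measure whether a cued pattern is held, which is how Hypothesis 1 defines performance.

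**The mean may work well.** A reader might infer from the 4-5% figure that the mean has no power. That holds only if drift is symmetric about the cue, which makes mean frequency unrelated to drift by construction. If everyone drifts the same way from the cue, the mean has 95-96% power. The documents support neither pattern over the other. What stands is that the mean is reliable under only one of the three patterns tried.

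**Averaging per breath or per beat might bias the Hypothesis 2 comparisons.** A reader might infer this too, since the recordings are breath-by-breath and beat-by-beat. The documents do not support it. That wording describes the resolution of recording, and no section gives an averaging rule. Respiratory rate and minute ventilation are per-time quantities by name. Any shift in mean blood pressure is zero when RR interval and pressure swing 90 degrees apart and reverses in anti-phase, and the documents give no phase. The point should not be raised as a bias.

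**Conclusion.** The concern holds in this form: the stated analysis does not test Hypothesis 1, because it compares means within subjects and the hypothesis is about maintenance over time related to practice between people. This follows from the text alone and needs no assumption.

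The practical loss cannot be fixed from the documents. Under the assumed drift sizes, power of mean frequency runs from 4-5% to 95-96% depending on the direction of drift, while RMS deviation stays at 91-93% at a breath-noise SD of 0.005 Hz. These figures illustrate the choice of measure. They do not estimate the power of this study.

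Hypothesis 2 is not affected. Its outcomes (respiratory rate, blood pressure, tidal volume, minute ventilation) are levels, and a mean is a suitable summary for them.

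**What to change.** Add to Section 9, before the outcome data are examined, a paragraph for Hypothesis 1:

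- **Main measure.** For each participant and cued pattern, the RMS deviation of breath-by-breath frequency from the cued value. List the cued value of each pattern. If patterns are to be averaged, divide by the cue first, since the cues differ up to 0.25/0.08 = 3.1-fold.
- **Tidal volume.** A matching within-recording measure, such as the coefficient of variation, reported beside the mean volume so that steady but small volumes are visible.
- **Supportive.** The absolute slope over the recording. The signed slope should not be used, because opposite drifts in different people cancel (8-9% power in the third row of the table).
- **Number of tests.** Average the main measure across patterns, or name one pattern. Frequency and volume tested separately in five patterns would be 2 × 5 = 10 tests. Averaging leaves two.
- **Model.** Regress the measure on logged practice minutes as a continuous between-person predictor, together with level of injury, which Hypothesis 1 also names. Confirm that the log records minutes. If it records only sessions, use sessions and say so.

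The cost is a paragraph of text and a little more processing of the same recordings, with no added visits or measurements. The downside is one added predictor at N = 20: with two predictors and an intercept, 20 − 3 = 17 residual degrees of freedom remain, fewer if further covariates are kept or injury level has several categories.
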